Official Title: The Mathematics of Breast Cancer Overtreatment: Improving Treatment Choice Through Effective Communication of Personalized Cancer Risk

NCT: NCT03775213

Document Date: November 11th, 2022

Principal Investigator (PI): [name]
Duke University
[name]
[contact]

Table of Contents

Purpose of the Study.....	3
Background & Significance.....	3
Overtreatment in Breast Carcinoma in Situ (DCIS).....	3
Scientific Premise for Active Surveillance in DCIS.....	3
Empowering Patients through Personalized Decision Aids (DA).....	3
Design & Procedures.....	4
Introduction	4
Justification & Feasibility	4
Research Design	4
Expected Outcomes	5
Rigor and Transparency	5
Potential Problems & Alternative Approaches	5
Selection of Subjects.....	5
Subject Recruitment and Compensation	5
Subject's Capacity to Give Legally Effective Consent.....	5
Risk/Benefit Assessment.....	6
Benefits	6
Costs to the Subject	6
Data Safety and Monitoring.....	6
References	7
Appendix 1: Decision Support Tool Questionnaire.....	11

Purpose of the Study

Implement a RCT to test the main hypothesis that the use of personalized decision aids leads to (i) an increase in the proportion of women who would consider active surveillance as a viable management strategy for DCIS, and (ii) an increase in knowledge of the associated risk trade-offs.

The central hypothesis is that communication of model-based personalized risk projections leads to an improved understanding of the trade-offs associated with different management strategies for DCIS.

Background & Significance

Overtreatment in Breast Carcinoma in Situ (DCIS). Each year in the United States alone, approximately 60,000 women will be diagnosed with DCIS (10). More than 97% of diagnosed women will choose immediate treatment, either surgery alone, or surgery in combination with radiation or chemotherapy (11). Since it is estimated that only 20-30% of DCIS lesions eventually become invasive (12, 13), this year, as many as 45,000 women will undergo radical surgery for a lesion that would not cause any harm in their remaining lifetime. The treatments, and thus the consequences of current DCIS management, are similar to those of treatment for invasive cancers. Consequences include pain (14-16), reduced quality of life (17, 18), increased risk of angiosarcoma and ischemic cardiac disease (due to radiation) (19, 20).

Scientific Premise for Active Surveillance in DCIS. The concept of AS was introduced to manage prostate cancer, because many men die with their prostate cancer, rather than from it, and treatment can be associated with profound morbidity. In AS, definitive therapy is not implemented at diagnosis. Instead, decisions about whether and when to intervene are based on subsequent disease behavior during surveillance over time (21). The AS approach allows the biologic behavior of a monitored tumor to dictate therapy, thus effectively reducing overtreatment by reserving aggressive interventions only for those likely to derive benefit from them. Because it is a non-invasive lesion with unknown malignancy potential, DCIS is comparable to early-stage prostate cancers for which AS is effective. However, currently only 3% of patients diagnosed with DCIS elect AS (22). Retrospective studies suggest that surgery may not improve survival for low-grade DCIS (23); however, prospective data remain scarce.

Empowering Patients through Personalized Decision Aids (DA). In the absence of prospective data for AS in patients with DCIS, the current paradigm of surgical treatment is unlikely to change in the near future. Since randomized controlled trials (RCTs) on AS have only recently started (7-9), relevant data is a long way off. At the same time, there is a great wealth of existing clinical and biological data on DCIS. However, because these resources are dispersed across a large number of data and knowledge sources, they remain largely inaccessible to patients and their physicians. To overcome this information barrier, the proposed research is expected to yield the best-possible individualized risk and uncertainty projections for patients diagnosed with DCIS, and to effectively communicate these projections via personalized DAs. This contribution is significant because it is expected to enable future DCIS patients to evaluate the trade-offs associated with different management strategies, and to make an informed decision that is aligned with their personal risk tolerance. By increasing the acceptability of AS through effective communication of personalized risks, the proposed research has a significant impact on the NIH's mission to reduce morbidity and enhance health.

Design & Procedures

Implement an RCT to test the main hypothesis that the use of personalized decision aids leads to (i) an increase in the proportion of women who would consider active surveillance as a viable management strategy for DCIS, and (ii) an increase in knowledge of the associated risk trade-offs. The consents and associated documents will be uploaded for review and approval before recruitment/consent.

Introduction. The objective of this study is to evaluate the impact of the DA on the understanding and acceptability of AS. For ethical reasons, we will test the main hypothesis in a hypothetical scenario in women without a personal history of cancer. The rationale for this aim is that, if successful in women with no personal history of cancer, we will advance towards the long-term goal of reducing overtreatment of DCIS. This aim will be informed by both the cognitive interviews (Aim R2a) and DA pre-testing (Aim R2c). All documents that will be used during this aim will be uploaded to this application once they are developed. We will submit modifications before beginning any data collection. Materials and consent documents will be developed for both the 202 participants for the RCT as well as for the beta-testing portion. All documents will be uploaded to the IRB once they are developed. No participants will be recruited/consented until an amendment is reviewed and approved by the IRB.

Justification & Feasibility. Because there is no clear distinction between attitude and choice in a hypothetical scenario, the commonly used evaluation measure of informed choice (39, 48) is unsuitable. We focus instead on the proportion of women who would choose AS as their preferred treatment option. Our working hypothesis is that the personalized DA will increase this proportion, because DCIS-specific mortality under AS is comparable to early-stage prostate cancer-specific mortality under AS (49), and 35-50% of men diagnosed with early-stage prostate cancer choose AS (50-52). Thus, it is plausible that AS could be considered a viable option for DCIS if the trade-offs for different management strategies are effectively communicated. Similar to previous DA evaluations (40, 53), we will use an RCT design. Since many women are unaware of AS in breast cancer (54), the control arm plays a crucial role by accounting for potential novelty priming.

Research Design. A parallel-arm double-blind RCT of 202 women to evaluate DST (decision support tool) with AS as an option (intervention) vs. DST without AS as an option (control) for a hypothetical diagnosis with low-grade DCIS. The primary outcome is treatment choice (binary: AS vs non-AS). Secondary outcomes include: acceptability of the different treatment options; perceived riskiness of the AS option, and pre- vs post-knowledge about DCIS (self-reported). Using the secure web portal REDCap, eligible consented women will complete three phases: randomization, baseline, and endline. Randomization phase: 1:1 randomization to control (surgery options only) or intervention (surgery options plus active surveillance option) arms, stratified by age group (< 65, 65+) to ensure balance of age-specific mortality risks. Block randomization (k=6) will be used. Baseline phase: all women will receive information about a hypothetical DCIS diagnosis and complete: 1) a baseline questionnaire about breast cancer and DCIS knowledge. Endline phase: after self-directed exploration of provided content, primary and secondary outcomes will be measured by questionnaire. A series of additional covariates and personality scales will also be elicited with the questionnaire. Each woman is expected to take at most one hour to complete the entire study task. In addition to the questionnaire, the team will collect basic website user analytics such as the order in which the website is explored, and how long participants spend on each page. Eligibility. Consented female participants of age 50-79 years, with no history of breast cancer and with a negative mammographic screen within the preceding 12 months. A financial incentive will be provided. Beta-testing. Before roll-out of the RCT, beta-testing of the evaluation will be conducted in 30 women (15 in each trial arm).

Expected Outcomes. An RCT-validated DA that improves understanding of the trade-offs associated with different management strategies for DCIS, and that increases acceptability of AS as a viable management strategy.

Rigor and Transparency. Rigor in DA evaluation is achieved by using a parallel-arm, double-blind randomized controlled trial design. Highest possible robustness and transparency of the approach will be achieved by registering the trial with clinicaltrials.gov and adhering to CONSORT guidelines for analysis.

Potential Problems & Alternative Approaches. Our working hypothesis is that the use of a personalized DA will increase the proportion of women who consider AS a viable management strategy for DCIS. Although our model projections (60) solidly support this hypothesis, it may not be confirmed here. In this unlikely case, we will analyze secondary outcomes and baseline risk measures to determine whether the lack of effect was due to poor understanding of DA content or was associated with low personal risk tolerance. Because the DA provides projections for all management modalities, it remains valuable even for women who are opposed to AS.

Selection of Subjects

Sex: Female

Age: 50-79 years

Has had a negative mammographic screen in the past 12 months

No personal history of breast cancer

Subject Recruitment and Compensation

For beta-testing (n=30) and the full randomized study (n=202), a total of 232 women will be recruited from the Duke Mammography Clinic. We will use a MaestroCare MyChart recruitment invitation to help identify potential participants. Potential subjects are identified via a report generated within MaestroCare by the DOCR MaestroCare Analyst team. A recruitment invitation will be sent by a DOCR analyst to potential subjects via MyChart. The patient will indicate if they are interested and the study coordinator will be sent an Inbasket message (MaestroCare internal message) if they are interested. Only key personnel who are delegated the task of patient identification/recruitment will have access to the Inbasket messages. Only patients who express interest will be contacted by key personnel, who will then follow the recruitment process approved by the IRB for this study. The study coordinator may follow-up (up to 3 times) with patients (by phone, email, or via MyChart message) if they expressed initial interest in the study. Patients who have opted out of research contact, via yellow dot in Maestro, will not be contacted. Patients will not be contacted more than three times, including via phone and email. If a patient states they would like to opt out, the study team will follow the Duke Recruitment and Engagement policy.

RCT beta-testing and randomized study compensation: \$25/survey

Subject's Capacity to Give Legally Effective Consent

Not applicable, only subjects capable of giving consent themselves will be eligible for inclusion in the study.

Risk/Benefit Assessment

The potential risks to RCT participants (Aim R3) include accidental disclosure of their identity or identifiable responses. This would result in the disclosure of the participant's identity, their opinion about the utility of the decision aid for communicating risk, and the self-reported effect of decision aid material on their perceived acceptability of active surveillance as a management strategy for DCIS. Because the participants have had a negative mammogram within the past 12 months and have no personal history of breast cancer, the risks of psychological harms by engaging with the decision aid content is expected to be minimal. Because there are few anticipated risks, in our opinion, the benefits driven from the causally strong conclusions of the trial outweigh the very minimal risks to the participants.

Only self-reported participant data and basic demographics will be collected for this study. The planned procedures for protecting against and minimizing potential risks include: use of a secure system for data collection; storage of data in a secure relational database requiring two-factor authentication.

Benefits:

Potential direct benefits of the research to research participants include intellectual satisfaction in participating in the pre-testing of a decision aid for breast cancer patients, and the satisfaction of contributing to the advancement of knowledge about decision aid development for breast cancer patients. The benefits to cancer care and society include the potential to generate new knowledge about informed decision making, and the potential for this work to steer future research in the management of breast carcinoma in situ. The minimal risks to subjects are considered reasonable in relation to the anticipated benefits to research participants and society overall.

Costs to the Subject

There are no costs that the subject will incur as a result of participation

Data Safety and Monitoring

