Appendix 1: Decision Support Tool Questionnaire

[figure not shown]
Survey: Decision support website

In this survey, we will ask you to explore a decision support website.

The website is designed for patients diagnosed with ductal carcinoma in situ (abbreviated as DCIS). It is okay if you have never heard of DCIS before. The website will provide plenty of information about it.

After exploring the website, you will be asked to answer questions about your experience and what you learned.

[figure not shown]
2 One quick note before you get started: Please be sure you are on a laptop or desktop computer (not a tablet or phone), using one of the browsers listed below. Microsoft Explorer is not supported.

- o Google Chrome (Windows/Mac): Install Chrome
- o Apple Safari (Mac): Install Safari
- o Microsoft Edge (Windows): Install Edge

Please remember that to receive compensation for this study, you need to complete the survey. Information to provide compensation will be collected at the end of the survey.

Before exploring the website, we have a couple of questions to help us understand how much you currently know about breast cancer and DCIS.

Please rate on the scale, how much do you know about breast cancer?

- 1 I know very little about breast cancer
- 2
- 3
- 4
- 5 I know a lot about breast cancer

Please rate on the scale, how much do you know about ductal carcinoma in situ, abbreviated as DCIS?

- 1 I know very little about DCIS
- 2
- 3
- 4
- 5 I know a lot about DCIS

0% 12% 100%

For this study, we would like you to imagine you were just diagnosed with DCIS.

With this in mind, we will ask you to carefully explore the DCIS website. To make your life easier, we will show you the website content in three separate links on the following pages.

When you are done exploring all three sections of the website, you will be asked to make a treatment decision.

Below is the link to the first section to explore, the Guide. It will open in a new window. When you are done exploring, return back here and click 'Next Page.'

Please click the link below and use the following access code: [record-name]

[Click Here \(Link 1 of 3\): Guide](#)

Below is the link to the second section to explore, the Decision Support Tool. It will open in a new window. When you are done exploring, return back here and click 'Next Page.'

Please click the link below and use the following access code: [record-name]

[Click Here \(Link 2 of 3\): Decision Support Tool](#)

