- Rarely
- Sometimes
- Often

How often do you think carefully about whether health information makes sense in your particular situation?

- Rarely
- Sometimes
- Often

How often do you try to find out whether information about your health can be trusted?

- Rarely
- Sometimes
- Often

Are you the sort of person who might question your doctor or nurse's advice based on your own research?

[figure not shown]
- Rarely
- Sometimes
- Often

0%

63%

100%

On the graph below, you see the percentage of people that die from different forms of cancer.

[figure not shown]
[figure not shown]

Approximately what percentage of people who die from cancer die from colon cancer, breast cancer, and prostate cancer taken together?

- 100%
- 25%
- 75%
- 50%
- Can't say

0% 66% 100%

In a magazine, you see two advertisements, one on page 5 and another on page 12. Each is for a different drug for treating heart disease, and each includes a graph showing the effectiveness of the drug compared to a placebo (sugar pill).

[figure not shown]

Compared to the placebo, which treatment leads to a larger decrease in the percentage of patients who die?

- Crosicol
- Hertinol
- They are equal
- Can't say

0% 69% 100%

The following figure shows the number of men and women among patients with disease X. The total number of circles is 100.

[figure not shown]
[figure not shown]

How many more men than women are there among 100 patients with disease X?

- 100
- 60
- 40
- 20
- 80
- Can't say

0% 72% 100%

In the newspaper you see two advertisements, one on page 15 and another on page 17. Each is for a different treatment of psoriasis, and each includes a graph showing the effectiveness of the treatment over time.

Which of the treatments contributes to a larger decrease in the percentage of sick patients?

- Apsoriatin
- Nopsorian
- They are equal
- Can't say

Sometimes, medical action is clearly necessary, and sometimes it is clearly not necessary. Other times, reasonable people differ in their beliefs about whether medical action is needed.

In situations where it's not clear, do you tend to lean towards taking action or do you lean towards waiting and seeing if action is needed?

- I strongly lean toward waiting and seeing
- I lean toward waiting and seeing
- I somewhat lean toward waiting and seeing
- I somewhat lean toward taking action
- I lean toward taking action
- I strongly lean toward taking action

Taking risks makes life more fun.

- 1 Strongly disagree
- 2
- 3
- 4

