	Overall	Intervention	Control	p-value
Demographics				
Age (mean, SD)				
Age group				
<65				
≥ 65				
Sex (Female, N (%))				
Age (mean, SD)				
Race/Ethnicity				
African-American / Black				
American Indian or Alaska Native				
Asian or Pacific Islander				
Hispanic				
White				
Marital Status				
In a relationship				
Married				
Divorced				
Separated				
Single				
Other				
Education				
High school or less				
Some college				
College graduate				
Post-graduate degree				
Rural (N, %)				
Cancer History				
Maximizer Minimizer Scale (mean, SD)				
General pre-tool Knowledge (mean, SD)				
Breast Cancer				
DCIS				
Additional Scales (TBD)				

Table 2. Primary and secondary outcomes at each time point, by treatment arm

	Control	Intervention
Primary Outcome		
Treatment Choice (AM, N, %)		
Secondary Outcomes		
AM Acceptability (mean, SD)		
AM Perceived Risk (mean, SD)		
Mastectomy uptake (N, %)		
Change in self-perceived DCIS knowledge (post-pre, mean, SD)		

Table 3. Intervention Effects on primary and secondary outcomes

	Intervention Effect Overall		Intervention effect: <65 years		Intervention effect: ≥65 years	
Primary Outcome	RR (95%CI)	ARR (95% CI)	RR (95%CI)	ARR (95% CI)	RR (95%CI)	ARR (95% CI)
Choose AM at post-tool						
Risk ratio (95% CI)						
Absolute risk (95% CI)						
	Intervention Effect		Intervention effect: <65 years		Intervention effect: ≥65 years	
Secondary Outcomes	β (95% CI)	aβ (95% CI)	β (95% CI)	aβ (95% CI)	β (95% CI)	aβ (95% CI)
AM Acceptability						
AM Risk						

RR, relative risk; ARR, adjusted relative risk. Adjusted models include [covariate list] as covariates

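### The fallback plan for a null result relies on baseline measures of risk tolerance, but every such item is asked after the tool and the treatment choice, so it can show association only

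*Protocol*

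**What the plan says.** Protocol, Potential Problems & Alternative Approaches, covers the case where the decision aid does not raise the proportion favouring active surveillance (active monitoring, AM, in the SAP). There "we will analyze secondary outcomes and baseline risk measures to determine whether the lack of effect was due to poor understanding of DA content". The second explanation to be examined is worded this way: "or was associated with low personal risk tolerance".

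Protocol, Research Design, has women in the baseline phase "complete: 1) a baseline questionnaire about breast cancer and DCIS knowledge". That is item 1, and no item 2 is listed. After describing the endline phase it adds: "A series of additional covariates and personality scales will also be elicited with the questionnaire".

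Appendix 1 opens with "Before exploring the website, we have a couple of questions to help us understand how much you currently know about breast cancer and DCIS", followed by one rating for each topic. The maximizer-minimizer item comes much later: "In situations where it's not clear, do you tend to lean towards taking action or do you lean towards waiting and seeing".

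SAP section J labels the maximizer-minimizer scale post-tool. It gives no timing for the attitude-to-risk scale and refers to the survey. The SAP Table 1 shell includes a row that begins "Maximizer Minimizer Scale (mean, SD", in a table with a p-value column.

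**The concern.** A measure used to explain an outcome should be fixed before the exposure and before the outcome. Here the risk-attitude answers come after both. A woman who has chosen surgery and written down why may then describe herself as someone who takes action. Her apparent attitude would in part repeat her choice. The maximizer-minimizer item is the most exposed, because acting versus waiting closely parallels surgery versus AM. Protocol, Justification & Feasibility, itself says that attitude and choice are hard to separate in a hypothetical scenario.

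At stake is what the trial may conclude after a null result. A report that risk-averse women declined AM would read as an explanation, although the design cannot establish the direction. SAP Exploratory Aim 3 (maximizer-minimizer score and choice) has the same limit, as do the risk-attitude items in Aim 5. In Table 1, a post-tool scale tested beside demographics and pre-tool knowledge reads as a check on randomisation, which it is not.

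**Working it through.** The plan attaches no figure to this analysis, so there is none to reproduce. The main check is the order of items in Appendix 1.

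**Item order**

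| Step | Content | Position |
|---|---|---|
| 1 | Self-rated knowledge of breast cancer and of DCIS (2 items) | before Link 1 |
| 2 | Guide, Decision Support Tool, Information Center | Links 1 to 3 |
| 3 | Treatment choice (primary outcome) | between the 18% and 21% marks |
| 4 | Written reasons; confidence | between the 21% and 24% marks |
| 5 | Acceptability, perceived AM risk, post-tool knowledge rating, website ratings, knowledge test, preparation scale | after the 24% mark |
| 6 | Health literacy, then graph literacy | around the 60% to 72% marks |
| 7 | Maximizer-minimizer (1 item), then attitude to risk (8 items) | after the 72% mark |
| 8 | Pain, appearance, cancer worry (3 worry items) | after step 7 |

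Pre-tool items: 2, both on knowledge. Pre-tool risk-tolerance items: 0. The protocol lists randomisation before baseline and the SAP lists it after. On either order the risk items follow randomisation, tool and choice.

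**How much could an echo of the choice matter?** The documents give no estimate, so this is an illustration. Assumptions: 202 women; a 6-point item generated as a normal variable with mean 3.5 and SD 1.3, rounded and truncated to 1–6; no true association; having chosen AM lowers the answer by a fixed shift; two-sided t-test at 5%. Share of trials with a significant association:

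| Choosing AM | No shift | 0.25 point | 0.5 point | 0.75 point |
|---|---|---|---|---|
| 5% | 5% | 9% | 20% | 40% |
| 15% | 5% | 16% | 46% | 80% |
| 25% | 5% | 21% | 61% | 92% |

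Uptake is itself uncertain. SAP section E assumes about 5% in the control arm, while section K.2 expects more than 10%.

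**Table 1.** An echo reaches the arm comparison only through the difference in choice: arm difference = shift × (intervention uptake − control uptake). With SAP Scenario 1 and a 0.5-point shift this is 0.5 × (0.20 − 0.05) = 0.075 point. Under the same assumptions, the Kruskal-Wallis test of SAP section K.1 rejects in about 7% of trials at a 0.5-point shift and 9% at 0.75, against 5% with none.

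A non-significant p-value would not be reassuring either. For a direct effect of the tool on the scale, the difference detectable with 80% power at 101 per arm is (1.960 + 0.842) × √(2/101) = 0.39 SD. At 0.2 SD, power is about 30%.

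**The case against.** The other side has four good arguments.

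- **Traits may be stable.** The eight attitude-to-risk items are general, and participants are told to think about themselves and their own experience. Much of the survey separates them from the choice. A reader might infer that the fallback question cannot be answered at all. The documents do not support that: an association can still be reported. The half of the sentence about poor understanding is also unaffected, because understanding of the tool has to be measured after it.
- **Some baseline data exist.** Pre-tool knowledge is a true baseline measure, and age is known from recruitment. The gap is in risk tolerance only.
- **The simulation assumes the echo that it detects.** A reader might take the larger percentages as expected false-positive rates. They are not: neither the shift nor the SD comes from the documents, and with no shift the rate is 5%. The model also covers the one maximizer-minimizer item, not the eight-item scale closest to personal risk tolerance.
- **Late placement has a reason.** Asking about waiting versus acting just before the tool could prime the primary outcome. Only the intervention arm receives in-depth AM information, so priming could interact with arm, and a change in overall uptake would change power.

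A reader might also infer that Table 1 would be visibly distorted. Through choice alone it would barely move. The table is titled as patient characteristics, and marital status and education are also asked at the end, but the tool can hardly change those.

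All of this narrows the consequence. It does not make the measures baseline, and the protocol promises to determine a reason, which goes beyond describing an association.

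**Conclusion.** The plan is wrong as written, and the error is minor. The protocol's fallback names a measure that the survey does not collect at baseline. The SAP's own post-tool label sits badly with the row in Table 1. The risk-attitude and maximizer-minimizer answers may show an association with choice; they cannot determine why a null result occurred. The same limit holds for Exploratory Aim 3 and for the risk-attitude items in Aim 5.

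The conclusion about timing rests on item order alone. How far answers might shift is unknown, and the simulated range shows only that a modest shift could matter. The Table 1 issue is chiefly one of labelling. The primary analysis is not affected.

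**What to change.** 1. In Protocol, Potential Problems & Alternative Approaches, replace the reference to baseline risk measures with post-tool risk-attitude measures. Say that they will be examined for association with choice and will not be used to establish the cause of a null result.
2. In the SAP, take the maximizer-minimizer scale out of the Table 1 comparison. Alternatively, report it separately by arm, labelled post-tool and without a balance p-value.
3. State the timing of the attitude-to-risk scale in SAP section J, and the same limit on inference under Exploratory Aims 3 and 5.

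These are text edits, with no new items or data.

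Optional, if the survey can still be changed: ask the eight general attitude-to-risk items before Link 1. This reorders existing questions and would give a true baseline measure. The downside to name is possible priming of the primary outcome, which cannot be assumed equal in the two arms. That risk is greater for the maximizer-minimizer item, so leaving it after the choice, correctly labelled, is defensible.

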- Used Mantel-Haenzel test (note: Table below created with power.prop.test in R)
- Scenario 1: we have 90% power with n=101 in each arm
- Scenario 2: if Δ is still 15% but control/intervention at 10%/25% we still have 80% power
- Scenarios 3-6: if, as estimated in usability testing, uptake of AM is 40%, then for Δ of 15%, 20%, 25% and 30%, we have power of 62%, 88%, 98% and 99%

Scenario	n (per arm)	P1	P2	Δ	Power
1	101	5%	20%	15%	90%
2	101	10%	25%	15%	80%
3	101	10%	40%	30%	99%
4	101	15%	40%	25%	98%
5	101	20%	40%	20%	88%
6	101	25%	40%	15%	62%

Randomization

- We prepare two separate random streams, one for younger (<65 years) and one for older (≥ 65 years) participant strata.
- Each stream is block randomized, with block size $k=6$.
- For each consented participant, we check for survey completion. Survey completion is defined as:
 - Reached the end of the survey (and thus were paid); and
 - Answered the treatment choice question (primary outcome); and
 - Answered the treatment acceptability questions (n=4; secondary outcome); and
 - Answered perceived riskiness question (secondary outcome); and
 - Answered both pre- and post-tool self-reported knowledge questions about DCIS (secondary outcome); and
 - Clicked on the Guide and the Decision Support Tool links provided in the survey.
- We continue to randomize until we reach n=101 participants (per arm) who pass the survey completion check.

F. Study Sample

Potential patients will be identified through Duke electronic health record system Epic and invited through the MyChart patient portal. Duke has an “opt-out” system that allows patients to be contacted directly about research studies for which they may be eligible. If a patient agrees to participate in the study by replying to a MyChart message, the patient will be consented and referred to the survey link.

Inclusion criteria

- Female
- Age 50-79

- No history of DCIS/breast cancer [medical record only]
- Negative mammogram in past 12 months [medical record only]

G. Outcomes & Hypotheses

Primary Outcome: Post-tool choice of active monitoring (AM). Presented to participants as a categorical item: active monitoring, lumpectomy, lumpectomy with radiation, mastectomy. Recorded for analysis as binary: AM vs non-AM.

Q1: If you were a patient diagnosed with DCIS, what treatment option would you choose?

[Order is randomized]

- Active monitoring
- Lumpectomy
- Lumpectomy with radiation
- Mastectomy

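### The mammogram criterion is met by any negative screen in the past 12 months, so as written it admits a woman with a later abnormal result or a pending biopsy (minor participant-protection gap)

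*Protocol*

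**What the plan says.** The mammogram criterion is stated three times:

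- Protocol, *Selection of Subjects*: "Has had a negative mammographic screen in the past 12 months".
- Protocol, *Research Design* (Eligibility): women "with no history of breast cancer and with a negative mammographic screen within the preceding 12 months".
- SAP section F, inclusion criteria: "Negative mammogram in past 12 months [medical record only" (the closing bracket follows in the SAP).

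The companion criterion in the protocol list is "No personal history of breast cancer". SAP section F widens it to DCIS or breast cancer and again takes it from the medical record alone.

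On how candidates are found, *Subject Recruitment and Compensation* says "Potential subjects are identified via a report generated within MaestroCare". The logic of that report is not given.

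The *Risk/Benefit Assessment* expects little psychological harm, and its stated reason is that "the participants have had a negative mammogram within the past 12 months and have no personal history of breast cancer".

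The task itself is set in Appendix 1: "For this study, we would like you to imagine you were just diagnosed with DCIS".

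**The concern.** The criterion tests whether one negative screen exists within a window. The risk argument needs something slightly different: that the woman has no unresolved breast finding when she does the task. The two part company for a woman whose negative screen was followed, inside the same 12 months, by an abnormal or incomplete result or a biopsy order. She has no diagnosis, so the history criterion does not remove her.

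What is at stake is participant protection. An exercise built around a newly diagnosed DCIS is a different experience for someone waiting to learn whether she has it, and the stated ground for calling the psychological risk minimal does not cover her.

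**Working it through.** The plan gives no figure on this point, so the main check is a reading of the text. Take a woman aged between 50 and 79 with a negative screen 10 months ago, an abnormal or incomplete mammogram last month, a biopsy pending and no diagnosis.

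| Stated rule | Where | Met? |
|---|---|---|
| Female, 50-79 | Protocol *Selection of Subjects*; SAP F | Yes |
| No history of breast cancer (SAP: or DCIS) | Same | Yes, nothing has been diagnosed |
| Negative mammogram within 12 months | Same, and *Research Design* | Yes, through the screen 10 months ago |

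She meets every written criterion. Next, does any other described step stop her?

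- **Record report.** Its query is not described. It might return the latest result or any result in the window.
- **Contact process.** *Subject Recruitment and Compensation* allows up to three follow-ups after a woman expresses interest. No re-check of the record before the survey is described.
- **Self-report.** SAP F marks both the mammogram and the history criteria as taken from the record only. The Appendix 1 questionnaire has no item on a recall, an abnormal result or a pending biopsy. Its item on past cancer comes near the end, after the imagined diagnosis and the treatment choice.
- **Description of the sample.** SAP section D calls participants healthy. That shows the intent, but it is not a criterion.

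No described step excludes her.

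**Size.** The number recruited is 30 (beta-testing) + 202 (trial) = 232, which agrees with the protocol. The share *p* of women with a work-up still open at the survey is not in the documents, so it has to be assumed. The expected number is 232 × *p*:

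| Assumed *p* | Expected women among 232 |
|---|---|
| 0.1% | 232 × 0.001 = 0.2 |
| 0.5% | 232 × 0.005 = 1.2 |
| 1% | 232 × 0.01 = 2.3 |

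These shares are illustrations, not estimates.

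**Effect on the comparison.** Eligibility does not depend on arm and allocation is 1:1 within age strata, so randomisation spreads such women over both arms. The sample size of 101 per arm is calculated from assumed uptake proportions and does not involve this criterion.

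**The case against.** The strongest reply is that a summary protocol's silence does not show that a check is missing. The report may already select on the latest result. The protocol also says that staff follow an IRB-approved recruitment process, which is not among these documents. That stands: it cannot be said that the rule will be applied literally. What can be said is that the written rule does not require the check. If practice is already stricter, the change only records it.

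The reply also notes other safeguards. Participation is voluntary, the survey announces its DCIS topic at the start, and *Data Safety and Monitoring* relies on the hypothetical scenario, best-practice development and adverse-event reporting as well. These reduce the concern but do not replace the argument made from the criterion.

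A reader might also infer four stronger points, which the documents do not support:

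- **That her answer does not measure the planned outcome.** The treatment-choice item is conditional on being a patient with DCIS. An undiagnosed woman answers it hypothetically like anyone else, and the protocol's requirement of a hypothetical scenario in women without a cancer history is still met.
- **That the arm comparison is biased.** Randomisation answers this.
- **That several such women are almost certain to be enrolled.** Assuming that 2-10% have further imaging and that 10-30% of those results are abnormal or unresolved gives 0.2-3%, or about 0.5 to 7 of 232. Both inputs are invented. The product also counts women already cleared by the time of the survey, and women already diagnosed, whom the history criterion excludes. It is a ceiling on its own assumptions.
- **That the tool would sway a real treatment decision.** Nothing in the documents bears on this.

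**Conclusion.** The gap is real on the text, and minor. All three statements of the criterion admit a woman with a later abnormal or incomplete result or a pending biopsy, and the reasoning in the *Risk/Benefit Assessment* does not hold for her. The number affected is unknown and probably very small. The 0.2 to 2.3 women above rest entirely on the assumed shares of 0.1% to 1%. This is a point about participant protection and the wording of an eligibility rule. It does not threaten the primary result.

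**What to change.** In Protocol *Research Design* and *Selection of Subjects*, and in SAP section F, replace the criterion with one on these lines: *the most recent breast imaging in the record is negative and dated within the past 12 months, with no later abnormal or incomplete result and no breast biopsy pending.* Apply it in the existing record report, run close to the time the survey link is sent.

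A record filter misses work-ups recorded elsewhere or begun after the link goes out. So add one screening question before the task, asking whether the woman is awaiting further breast tests or results. Put it ahead of arm assignment, so that nobody is excluded after randomisation. The placement needs stating because the protocol lists randomisation before the baseline phase, whereas SAP section D puts the baseline survey first.

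The cost is one added condition in the report, one question and a sentence in each document. The downside is a few candidates lost before randomisation.
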